5 STUDY DRUG

This is a non-blinded study which includes investigational products:

Product	Potency	Appearance	Packaging	Storage Conditions
Nivolumab (Solution for Injection)	10 mg/mL	Clear to pale yellow liquid; may contain particles	10 mL/vial	Store at 2-8°C; protect from light or freezing
Ipilimumab (Solution for Injection)	5 mg/mL	Clear to pale yellow liquid; may contain particles	10 mL/vial	Store at 2-8°C; protect from light or freezing

Premedications or medications used to treat infusion-related reactions should be sourced by the local site. Solutions used as diluents (0.9% Sodium Chloride or 5% Dextrose) should also be sourced by the local site.

5.1 Investigational Product

An investigational product, also known as investigational medicinal product in some regions, is defined a pharmaceutical form of an active substance or placebo being tested or used as a reference in a clinical study, including products already with a marketing authorization but used or assembled (formulated or packaged) differently than the authorized form, or used for an unauthorized indication, or when used to gain further information about the authorized form.

The investigational product should be stored in a secure area according to local regulations. It is the responsibility of the investigator to ensure that investigational product is only dispensed to study subjects. The investigational product must be dispensed only from official study sites by authorized personnel according to local regulations.

In this protocol, investigational products are: nivolumab and ipilimumab.

5.2 Non-investigational Product

Not applicable.

5.3 Storage and Dispensing

The product storage manager should ensure that the study drug is stored in accordance with the environmental conditions (temperature, light, and humidity) as determined by BMS. If concerns regarding the quality or appearance of the study drug arise, the study drug should not be dispensed and contact BMS immediately.

Study drug not supplied by BMS will be stored in accordance with the package insert.

Investigational product documentation (whether supplied by BMS or not) must be maintained that includes all processes required to ensure drug is accurately administered. This includes documentation of drug storage, administration and, as applicable, storage temperatures, reconstitution, and use of required processes (eg, required diluents, administration sets).

Infusion-related supplies (eg, IV bags, in-line filters, 0.9% sodium chloride injection, 5% dextrose

injection) will not be supplied by the sponsor and should be purchased locally if permitted by local regulations.

Please refer to the current version of the Investigator Brochure (IB) and/or pharmacy reference sheets for complete storage, handling, dispensing, and infusion information for nivolumab and ipilimumab.

The infusion duration of nivolumab is 30 minutes and for ipilimumab 30 minutes.

5.4 Method of Assigning Subject Identification

After a subject's initial eligibility is established and informed consent obtained, subjects will be assigned a study number/ID. Once enrolled and study number assigned, patients will be randomized in a 1:1 ratio. The following information is required for subject randomization:

- Subject number
- Date of birth
- AJCC M classification

Subjects meeting all eligibility criteria will be randomized in a 1:1 ratio to Arm A (Nivo + Ipi) or Arm B (Nivo + Ipi + XRT) stratified by the following factors:

- Prior immunotherapy

5.5 SBRT and Drug Dosing Schedule

5.5.1 Dosing Schedule

First dose must be administered within 2 weeks following randomization. Subjects may be dosed up to ± 2 days before or after the scheduled date if necessary.

The Dosing schedule is described in [Table 5.5-1](#) and [Table 5.5-2](#).

	Week 1	Week 2	Week 3	Week 5
Arm A: Nivolumab+ Ipilimumab	240 mg Nivolumab + 1 mg/kg Ipilimumab		240 mg Nivolumab	240 mg Nivolumab
	Week 7			
	240 mg Nivolumab Every 2 weeks + 1 mg/kg Ipilimumab Every 6 weeks until progression or unacceptable toxicity			

	Week 1	Week 2	Week 3	Week 5
Arm A: Nivolumab+ Ipilimumab+ SBRT	240 mg Nivolumab + 1 mg/kg Ipilimumab	24Gy/3fx SBRT (may be completed by Week 3)	240 mg Nivolumab	240 mg Nivolumab
	Week 7			
	240 mg Nivolumab Every 2 weeks + 1 mg/kg Ipilimumab Every 6 weeks until progression or unacceptable toxicity			

If a subject cannot receive a dose within 2 days of its scheduled administration date, the dose should be completely omitted. When the subject is able to re-initiate treatment, dosing should resume at the time of the next scheduled dose. Missed doses will not be replaced.

5.5.2 *Antiemetic Premedications*

Antiemetic premedications should not be routinely administered prior to dosing of drugs. See [Section 5.5.8](#) for premedication recommendations following a nivolumab or ipilimumab related infusion reaction.

5.5.3 *Dose Modifications*

There will be no dose modifications permitted. Dose reductions or dose escalations are not permitted.

5.5.4 *Management Algorithms for Immuno-Oncology Agents*

Immuno-oncology (I-O) agents are associated with adverse events that can differ in severity and duration than adverse events caused by other therapeutic classes. Nivolumab and ipilimumab are considered immuno-oncology agents in this protocol. Management algorithms have been developed to assist investigators in assessing and managing the following groups of adverse events: Gastrointestinal, Renal, Pulmonary, Hepatic, Endocrinopathies, Skin, and Neurological. (Appendix 4)

Early recognition and intervention are recommended according to the management algorithms; and in addition include ophthalmologic evaluations for any visual symptoms in order to evaluate for nivolumab or ipilimumab related uveitis.

The recommendations are to follow the algorithms in the nivolumab investigator brochure for immune related events; while the ipilimumab investigator brochure contains similar algorithms, the algorithms in the nivolumab brochure have been aligned to accommodate combinations as well as nivolumab monotherapy.

Therefore, the algorithms recommended for utilization are attached for reference.

For subjects expected who require more than 4 weeks of corticosteroids or other immunosuppressants to manage an adverse event, consider the following recommendations

- Antimicrobial/antifungal prophylaxis per institutional guidelines to prevent opportunistic infections such as *Pneumocystis jiroveci* and fungal infections.
- Early consultation with an infectious disease specialist should be considered. Depending on the presentation, consultation with a pulmonologist for bronchoscopy or a gastroenterologist for endoscopy may also be appropriate.
- In patients who develop recurrent adverse events in the setting of ongoing or prior immunosuppressant use, an opportunistic infection should be considered in the differential diagnosis.

Additional details on the safety of nivolumab and ipilimumab , including results from clinical studies, are available in the IB.

5.5.5 *Dose Delay Criteria*

Because of the potential for clinically meaningful nivolumab-related AEs requiring early recognition and prompt intervention, management algorithms have been developed for suspected AEs of selected

categories.

Dose delay criteria apply for all drug-related adverse events (regardless of whether or not the event is attributed to nivolumab, ipilimumab or both). All study drugs must be delayed until treatment can resume.

Nivolumab and ipilimumab administration should be delayed for the following:

- Any Grade ≥ 2 non-skin, drug-related adverse event, with the following exceptions:
 - Grade 2 drug-related fatigue or laboratory abnormalities do not require a treatment delay
- Any Grade 3 skin, drug-related adverse event
- Any Grade 3 drug-related laboratory abnormality, with the following exceptions for asymptomatic amylase or lipase, AST, ALT, or total bilirubin:
 - Grade 3 amylase or lipase abnormalities that are not associated with symptoms or clinical manifestations of pancreatitis do not require a dose delay. It is recommended to consult with the principle investigator for Grade 3 amylase or lipase abnormalities.
 - If a subject has a baseline AST, ALT, or total bilirubin that is within normal limits, delay dosing for drug-related Grade ≥ 2 toxicity
 - If a subject has baseline AST, ALT, or total bilirubin within the Grade 1 toxicity range, delay dosing for drug-related Grade ≥ 3 toxicity
- Any adverse event, laboratory abnormality, or intercurrent illness which, in the judgment of the investigator, warrants delaying the dose of study medication.

5.5.6 Criteria to Resume Treatment

Subjects may resume treatment with study drug when the drug-related AE(s) resolve to Grade ≤ 1 or baseline value, with the following exceptions:

- Subjects may resume treatment in the presence of Grade 2 fatigue
- Subjects who have not experienced a Grade 3 drug-related skin AE may resume treatment in the presence of Grade 2 skin toxicity
- Subjects with baseline Grade 1 AST/ALT or total bilirubin who require dose delays for reasons other than a 2-grade shift in AST/ALT or total bilirubin may resume treatment in the presence of Grade 2 AST/ALT OR total bilirubin
- Subjects with combined Grade 2 AST/ALT AND total bilirubin values meeting discontinuation parameters (Section XX) should have treatment permanently discontinued
- Drug-related pulmonary toxicity, diarrhea, or colitis, must have resolved to baseline before treatment is resumed
- Drug-related endocrinopathies adequately controlled with only physiologic hormone replacement may resume treatment

If the criteria to resume treatment are met, the subject should restart treatment at the next scheduled timepoint per protocol. However, if the treatment is delayed past the next scheduled timepoint per protocol, the next scheduled timepoint will be delayed until dosing resumes. If the design of the study defines that doses may not be omitted [skipped], strongly recommend adding “Doses may not be skipped”

If treatment is delayed > 6 weeks, the subject must be permanently discontinued from study therapy, except as specified in discontinuation section.

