5.5.7 Discontinuation Criteria

Treatment should be permanently discontinued for the following:

- Any Grade 2 drug-related uveitis or eye pain or blurred vision that does not respond to topical therapy and does not improve to Grade 1 severity within the re-treatment period OR requires systemic treatment
- Any Grade 3 non-skin, drug-related adverse event lasting > 7 days, with the following exceptions for drug-related laboratory abnormalities, uveitis, pneumonitis, bronchospasm, diarrhea, colitis, neurologic adverse event, hypersensitivity reactions, and infusion reactions
 - Grade 3 drug-related uveitis, pneumonitis, bronchospasm, diarrhea, colitis, neurologic adverse event, hypersensitivity reaction, or infusion reaction of any duration requires discontinuation
 - Grade 3 drug-related laboratory abnormalities do not require treatment discontinuation except those noted below
 - Grade 3 drug-related thrombocytopenia > 7 days or associated with bleeding requires discontinuation
 - Any drug-related liver function test (LFT) abnormality that meets the following criteria require discontinuation:
 - AST or ALT > 8 x ULN
 - Total bilirubin > 5 x ULN
 - Concurrent AST or ALT > 3 x ULN and total bilirubin > 2 x ULN
- Any Grade 4 drug-related adverse event or laboratory abnormality, except for the following events which do not require discontinuation:
 - Isolated Grade 4 amylase or lipase abnormalities that are not associated with symptoms or clinical manifestations of pancreatitis and decrease to < Grade 4 within 1 week of onset.
 - Isolated Grade 4 electrolyte imbalances/abnormalities that are not associated with clinical sequelae and are corrected with supplementation/appropriate management within 72 hours of their onset
- Any dosing interruption lasting > 6 weeks with the following exceptions:

- Dosing interruptions to allow for prolonged steroid tapers to manage drug-related adverse events are allowed. Prior to re-initiating treatment in a subject with a dosing interruption lasting > 6 weeks, the Investigator must be consulted. Tumor assessments should continue as per protocol even if dosing is interrupted
- Dosing interruptions > 6 weeks that occur for non-drug-related reasons may be allowed if approved by the Investigator. Prior to re-initiating treatment in a subject with a dosing interruption lasting > 6 weeks, the Investigator must be consulted. Tumor assessments should continue as per protocol even if dosing is interrupted

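### Sections 5.5.6 and 5.5.7 overlap for severe endocrinopathy controlled on hormone replacement: one permits resumption, the other orders permanent discontinuation, and precedence is not clearly stated

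*Combined protocol and SAP*

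**What the plan says.** Section 5.5.6 opens with a general condition: "Subjects may resume treatment with study drug when the drug-related AE(s) resolve to Grade ≤ 1 or baseline value, with the following exceptions". One of the exceptions is "Drug-related endocrinopathies adequately controlled with only physiologic hormone replacement may resume treatment". That bullet mentions no grade, no duration and no other section.

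Section 5.5.7 begins "Treatment should be permanently discontinued for the following". Two of its entries matter here:

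- "Any Grade 3 non-skin, drug-related adverse event lasting > 7 days", followed by "with the following exceptions for drug-related laboratory abnormalities, uveitis, pneumonitis, bronchospasm, diarrhea, colitis, neurologic adverse event, hypersensitivity reactions, and infusion reactions". Among the details is "Grade 3 drug-related laboratory abnormalities do not require treatment discontinuation except those noted below"; the laboratory criteria then listed concern platelets and liver tests.
- "Any Grade 4 drug-related adverse event or laboratory abnormality, except for the following events which do not require discontinuation". The two exceptions are certain isolated electrolyte abnormalities and "Isolated Grade 4 amylase or lipase abnormalities that are not associated with symptoms or clinical manifestations of pancreatitis", the latter only if the value falls below Grade 4 within a week.

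Endocrinopathy is named in neither set of exceptions.

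Section 4.3 lists reasons for which subjects must stop investigational product. It includes further protocol-specified reasons and sends the reader to Section 4.5.7. The table of contents ends Section 4 at 4.4.2, so there is no such section.

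**The concern.** Section 5.5.6 is the page a site consults when deciding whether a delayed patient can restart. For an endocrinopathy it gives a permission that depends only on control by replacement. A site that stops reading there could restart a patient who has already met a permanent stop in Section 5.5.7.

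What is at stake is mainly safety, through re-exposure after a severe event that the protocol lists as a reason to stop. There is also consistency: both arms receive both drugs, the study is not blinded (Section 5), and the same event could be handled differently from site to site. That would affect drug exposure and the rate of discontinuation for toxicity, in a trial whose secondary objectives include comparing safety and tolerability between the arms.

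**Working it through.** No figure in the plan has to be reproduced. The check sets the two sections side by side, then sizes the problem roughly.

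**Case check.** Take a drug-related endocrinopathy that is controlled with replacement only.

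| Event | Section 5.5.6 | Section 5.5.7 | Result |
|---|---|---|---|
| Grade 2 | may resume | no grade-based trigger | consistent |
| Grade 3, 7 days or less | may resume | duration trigger not met | consistent |
| Grade 3, laboratory-only | may resume | exempt as a laboratory abnormality | consistent |
| Grade 3, clinical, more than 7 days | may resume | discontinue permanently | conflict |
| Grade 4 | may resume | discontinue permanently | conflict |

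The nine categories named after the Grade 3 rule should not be read as nine leniencies. Eight of them are stricter, since a Grade 3 event of that type stops treatment at any duration. Only the laboratory category is more lenient, and it is what removes the third row from the conflict.

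**How the other 5.5.6 exceptions are bounded.**

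- Fatigue is limited to Grade 2.
- Skin toxicity is limited to Grade 2 in patients with no previous Grade 3 drug-related skin event.
- The liver-test permission is limited to Grade 2 in patients with a Grade 1 baseline, and the combined liver-test bullet refers to the discontinuation parameters (through an unfilled section number).
- Pulmonary toxicity, diarrhea and colitis are given a condition that must be met before restarting, which is a requirement and not a permission.
- The rule on delays over 6 weeks defers to the discontinuation section.

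The endocrine bullet is the only event-specific permission with no such bound.

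**Size.** Inputs:

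- Planned patients at full accrual: 24 per arm (Section 9.1.1), so 2 × 24 = 48.
- Ipilimumab monotherapy at 3 mg/kg every 3 weeks: 3% Grade 3/4 immune-related endocrine disorders (Section 1.5.4).
- Nivolumab monotherapy: one Grade 3 event each of adrenal insufficiency, hyperthyroidism and hypothyroidism among 304 subjects (Section 1.5.4). This is 3/304 = 1.0% if they were three different people.
- This combination at this dose: no rate is given. A range of p = 1% to 4% is assumed; its upper end simply adds the two monotherapy figures.

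Expected number with any Grade 3/4 endocrine event = 48 × p. Chance of at least one = 1 − (1 − p)^48.

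| p (assumed) | Expected of 48 | Chance of at least one |
|---|---|---|
| 1% | 0.48 | 38% |
| 3% | 1.44 | 77% |
| 4% | 1.92 | 86% |

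These figures count any Grade 3/4 endocrine event. A conflict case must also be clinical and last more than 7 days if Grade 3, and must be controlled on replacement alone. The documents give no basis for that discount, so for each assumed p the table is an upper limit on conflict cases.

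**The case against.** The strongest reply is that the sections run in sequence: 5.5.5 covers delay, 5.5.6 restart after delay, and 5.5.7 permanent stopping. On this view the endocrine bullet relaxes only the recovery threshold for a delayed patient and was never an exception to 5.5.7. The wording helps: Section 4.3 says subjects must discontinue and 5.5.7 orders permanent discontinuation, while 5.5.6 only says a patient may resume. A site that discontinues complies with every section. The general 5.5.6 condition also supports this reading: taken literally, it would let a Grade 4 event that has resolved to Grade 1 restart, which 5.5.7 plainly does not intend. Finally, 5.5.7 lets the investigator stop treatment for substantial clinical risk.

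Much of this stands. A reader might infer an even contradiction with nothing to choose between the two rules. The documents do not support that, because their mandatory language leans towards discontinuation.

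The reply does not remove the ambiguity. The Section 4.3 pointer leads nowhere; 5.5.7 is presumably meant, but the reader has to guess. Section 5.5.6 writes its deferrals and limits into other bullets and leaves them out of this one, so a site could treat a specific permission for a named event as displacing a general stop. The section also retains a placeholder section number and a drafting note, which suggests unfinished text more than a deliberate hierarchy.

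The Appendix 4 endocrinopathy algorithm is a figure that was not legible in the text reviewed. That is not a fault of the plan. The legible notes beside it do not address discontinuation by grade, so the figure can neither settle the matter nor be counted against the protocol.

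**Conclusion.** The point holds within narrow limits. Sections 5.5.6 and 5.5.7 give different instructions for a clinical Grade 3 endocrinopathy lasting more than 7 days and for a Grade 4 endocrinopathy, once either is controlled on replacement. Discontinuation probably governs as the text stands, but no section says so in a way a site can follow. This is an inconsistency of wording with a safety consequence, not a flaw in the statistical design.

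Three broader inferences are not supported:

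- **That every controlled endocrinopathy is affected.** Grade 2 events, Grade 3 events of 7 days or less, and Grade 3 laboratory-only findings raise no conflict.
- **That 38% to 86% is the chance of a conflict case.** Those percentages, like the 0.5 to 1.9 expected patients, describe any Grade 3/4 endocrine event under assumed rates taken from monotherapy at other doses or schedules. Conflict cases are a subset of unknown size.
- **That PFS is biased.** Patients who stop for reasons other than progression stay under surveillance (Section 4.1), PFS counts progression or death (Section 9.2.2), and the rule is the same in both arms. Any effect through drug exposure is conjecture.

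The inconsistency itself rests on the text and on none of the assumed rates.

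**What to change.** Reconcile Sections 5.5.6 and 5.5.7 by one of two routes: confine the endocrine bullet in 5.5.6 to events that meet no 5.5.7 criterion, or name controlled endocrinopathy among the 5.5.7 exceptions. Either way, state which section takes precedence for endocrinopathies and for which grades, and check that the Appendix 4 endocrine algorithm agrees. Correct the Section 4.3 reference to 4.5.7 so that it points to the intended discontinuation section. Which rule applies is for the clinical team to decide.

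The cost is one clause and one corrected cross-reference. Sample size, error rates and analyses are unaffected.

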5.5.7 Discontinuation Criteria

Treatment should be permanently discontinued for the following:

- Any Grade 2 drug-related uveitis or eye pain or blurred vision that does not respond to topical therapy and does not improve to Grade 1 severity within the re-treatment period OR requires systemic treatment
- Any Grade 3 non-skin, drug-related adverse event lasting > 7 days, with the following exceptions for drug-related laboratory abnormalities, uveitis, pneumonitis, bronchospasm, diarrhea, colitis, neurologic adverse event, hypersensitivity reactions, and infusion reactions
 - Grade 3 drug-related uveitis, pneumonitis, bronchospasm, diarrhea, colitis, neurologic adverse event, hypersensitivity reaction, or infusion reaction of any duration requires discontinuation
 - Grade 3 drug-related laboratory abnormalities do not require treatment discontinuation except those noted below
 - Grade 3 drug-related thrombocytopenia > 7 days or associated with bleeding requires discontinuation
 - Any drug-related liver function test (LFT) abnormality that meets the following criteria require discontinuation:
 - AST or ALT > 8 x ULN
 - Total bilirubin > 5 x ULN
 - Concurrent AST or ALT > 3 x ULN and total bilirubin > 2 x ULN
- Any Grade 4 drug-related adverse event or laboratory abnormality, except for the following events which do not require discontinuation:
 - Isolated Grade 4 amylase or lipase abnormalities that are not associated with symptoms or clinical manifestations of pancreatitis and decrease to < Grade 4 within 1 week of onset.
 - Isolated Grade 4 electrolyte imbalances/abnormalities that are not associated with clinical sequelae and are corrected with supplementation/appropriate management within 72 hours of their onset
- Any dosing interruption lasting > 6 weeks with the following exceptions:

- Dosing interruptions to allow for prolonged steroid tapers to manage drug-related adverse events are allowed. Prior to re-initiating treatment in a subject with a dosing interruption lasting > 6 weeks, the Investigator must be consulted. Tumor assessments should continue as per protocol even if dosing is interrupted
- Dosing interruptions > 6 weeks that occur for non-drug-related reasons may be allowed if approved by the Investigator. Prior to re-initiating treatment in a subject with a dosing interruption lasting > 6 weeks, the Investigator must be consulted. Tumor assessments should continue as per protocol even if dosing is interrupted
- Any adverse event, laboratory abnormality, or intercurrent illness which, in the judgment of the Investigator, presents a substantial clinical risk to the subject with continued nivolumab or ipilimumab dosing

